#### 4.4.1 Subject Withdrawal Criteria

All subjects reserve the right to withdraw from the clinical study at any time, as stated in the informed consent form (ICF). The Investigator may discontinue subjects from the clinical study for any of the following reasons:

- ECG evidence of QT prolongation (QTcF > 530 msec, or an increase of QTcF > 60 msec above baseline to a value > 480 msec on the 12-lead ECG, confirmed on a repeat 12-lead ECG taken after resting at least 5 minutes in a supine or semi-recumbent position after the original finding of prolonged QTcF).
- 2. It is the Investigator's opinion that it is not in the subject's best interest to continue in the study.
- 3. Any subject who exhibits any Suicidal Behavior or Suicidal Ideation (e.g. subject answers "yes" to question 4 or 5 in the Suicidal Ideation section of the CSSRS). These subjects should be evaluated by a psychiatrist immediately.

- 4. Rash that is clinically significant and considered to be related to the study drug (e.g. morbiliform, urticarial, papular).
- 5. Subject experiences an SAE considered to be related to the study drug

# 4.4.2 Decisions to discontinue the study will be made at each participating site by the Principal Investigator. If feasible, the reason for discontinuation should be discussed with the Medical Monitor. Reasons for Discontinuation

The reason for withdrawal must be determined by the investigator and recorded in the subject's medical record and on the eCRF. If a subject is withdrawn for more than 1 reason, each reason should be documented in the source document and the most clinically relevant reason should be entered on the eCRF.

Reasons for discontinuation include but are not limited to:

- AE
- Protocol deviation
- Withdrawal of consent by subject
- Lost to follow-up
- Lack of efficacy
- Other (If "Other" is selected, the investigator must specify the reason on the eCRF)

#### 4.4.3 Subjects "Lost to Follow-up" Prior to Last Scheduled Visit

A minimum of 3 documented attempts must be made to contact any subject lost to follow-up at any time point prior to the last scheduled contact (office visit or telephone contact). At least 1 of these documented attempts must include a written communication sent to the subject's last known address via courier or mail (with an acknowledgement of receipt request) asking that she return to the site for final safety evaluations. If a contact is made but the subject refuses or is unable to come to the final safety evaluation it should be documented in the eCRF.

#### 5.0 PRIOR AND CONCOMITANT TREATMENT

All non-study treatments (including herbal treatments, vitamins, and non-pharmacological treatments) received within 60 days prior to the screening visit (Visit 1) and through the final study contact (including protocol-defined follow-up period) must be recorded on the appropriate eCRF page.

#### 5.1 **Prior Pharmacological Treatment**

Prior pharmacological treatment includes all treatments (including herbal treatments and vitamins) that the subject received and stopped within 60 days of the date of the screening visit. For example, if the subject had been treated with sertraline during pregnancy but it was discontinued 3 weeks prior to the screening visit, this medication would be recorded on the prior medication eCRF page.

#### 5.2 Concomitant Pharmacological Treatment

Concomitant treatment refers to all treatments (including herbal treatment and vitamins) taken between the screening visit and the end of the follow-up period regardless of the start date of the concomitant medication. For example, if the subject was started on a prenatal vitamin and it was continued through the study period, this treatment would be recorded on the concomitant medication eCRF page.

#### 5.3 Concomitant Psychological Treatment

Concomitant psychological treatment refers to all psychological care the subject is receiving between the screening visit and the end of the follow-up period regardless of the start date of the concomitant psychological treatment. Concomitant psychological treatment information must be recorded on the concomitant psychological treatments eCRF page.

#### 5.3.1 **Permitted Treatment**

#### 5.3.1.1 Permitted Psychological Treatments

The subject may continue their current form of psychological treatment (e.g. Cognitive Behavioral Therapy, Psychodynamic Psychotherapy, Supportive Psychotherapy) throughout the treatment period. However, initiation of a new therapy (a new treatment modality or switching a therapist) is prohibited between screening and discharge from the inpatient unit.

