#### 5.3.1.3 Other Permitted Treatments

The subject may continue her current non-psychiatric medications with the exception of medications that are strong inducers or inhibitors of CYP3A4 (Appendix 1).

The subject may use diphenhydramine 25 to 50 mg, trazodone 25 to 50 mg or doxepin 3 to 5 mg during the inpatient or outpatient phase for severe insomnia as needed. Only 1 dose of 1 of the medications is allowed per night. It is recommended to use the same medication each night. To minimize carryover effects there should be a minimum of 10-hour interval between administration of an allowed hypnotic and any efficacy assessment. Other hypnotics, such as zolpidem or zaleplon, are prohibited.

If the subject is treated with an atypical antipsychotic medication that was started with the purpose of augmenting the therapeutic effect of an antidepressant (i.e. the antipsychotic is not intended for treatment of psychosis or mood stabilization), she may continue this treatment throughout the study period. Examples of such treatments would be quetiapine 50 mg at bedtime and aripiprazole 15 mg daily. However, the antipsychotic medication must have been started at least 21 days before the screening, and there should not have been a dose change within 7 days of screening.

Other medications and medication combinations should be discussed with the medical monitor before enrolling the subject in the study.

After the subject completes the study treatment period, any changes to the antidepressant or antianxiety medication regimen are not prohibited, but investigators are encouraged to maintain such drugs at stable doses if possible. Any changes in the medication regimen must be recorded on the concomitant medication eCRF page.

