#### 5.3.2 **Prohibited Treatments**

The following classes of medications and treatments are prohibited during the study treatment period. If the subject has been taking any of these medications before enrollment, there should be a medication-free period of a minimum of 5 days or 5 half-lives of that medication, whichever is longer, before admission to the unit. In general, subjects who require extensive washouts may not be candidates for participation and those cases should be discussed with the medical monitor.

- Benzodiazepines and barbiturates
- Gabapentin and pregabalin
- Anticonvulsants and mood stabilizers
- All hypnotics and sleep aids (with the exception of low-dose diphenhydramine, doxepin, and trazodone as described above)
- Opioids

- Cannabis
- Electroconvulsive Therapy (ECT), rapid transcranial magnetic stimulation (rTMS), vagal nerve stimulation
- Experimental (including hormonal and herbal) treatments of postpartum depression
- Strong inhibitors and inducers of CYP3A4 (Appendix 1)

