# 7.0 STUDY PROCEDURES

This is a Phase 2A, double-blind, placebo-controlled, multiple-dose escalation study consisting of up to 6 cohorts. In Cohorts 1-5 the IV formulation of ganaxolone will be used while in Cohort 6 both IV and oral formulations will be used. Approximately 200 women with PPD 18 to 45 years of age will be screened to randomize approximately 100 subjects across the up to 6 cohorts. Approximately 10-30 subjects will be randomized into each cohort. Randomized subjects will receive ganaxolone or placebo in a 1:1 ratio. In Cohorts 1-5 the treatment is administered intravenously (with or without an initial bolus) over 60 hours. In Cohort 6 the treatment is initiated with a 6-hour intravenous (IV) infusion followed by oral ganaxolone or matching placebo. Additional subjects may be included into these cohorts or additional cohorts may be added, but will not exceed 100 randomized subjects for the study.

The screening period for each cohort will be up to 2 weeks. Following the screening period, there will be a 4-day inpatient treatment phase at a hospital or clinical pharmacology unit for Cohorts 1-5 during which a 60-hour infusion of ganaxolone or placebo will be administered (with or without bolus dosing). The subjects will be discharged from the unit on the morning of Day 4. There will be 2 safety follow-up visits after inpatient discharge on post-treatment Weeks 1 and 4.

[figure not shown]
In Cohort 6, following the screening period, there will be a 1-day inpatient treatment phase at a hospital or clinical pharmacology unit during which a 6-hour infusion of ganaxolone or matching placebo will be administered initially from 9 am to 3 pm ( $\pm$ 1 hour) before oral dosing is started at 7 pm ( $\pm$ 1 hour). The subjects will be admitted on Day 0 and discharged from the unit in the morning of Day 2. The first dose of oral ganaxolone (4 capsules; 900 mg) or matching placebo will be administered at dinner time (around 7 pm) of Day 1, 4 hours after the end of infusion on Day 1. Oral dosing is continued as outpatient on Days 2-28. The dosing regimen during the outpatient phase of Cohort 6 is 900 mg or placebo (4 capsules) at dinner time daily. A 3-day taper will follow at days 29, 30, and 31, as described in Section 3.4.6. There will be 3 safety follow-up visits after the last dose on post-treatment Weeks 1,4, and 6.

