### 7.6.2 **Visit 3 HAMD Call (Day +4 ±1 day)**

• CTNI to conduct HAMD17 interview

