### 9.5.8 Efficacy Analyses

### 9.5.8.1 Primary Endpoint

The primary efficacy endpoint will be HAMD17 total score change from baseline to 60 hours post-infusion (on Day 3) for Cohorts 1-3 and to Day 29 for Cohort 6. The primary analysis in each cohort will be done using the mITT set. Although the trial is not powered for inferential analysis and there is no consideration for control of type 1 error across multiple cohorts, a clinically meaningful numeric difference in means of 3-4 points between ganaxalone and placebo treatment groups would be considered an indication of efficacy and will be the most influential outcome in the overall assessment of the efficacy of ganaxalone in treating PPD.

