31	5.3.1.3 Other Permitted Treatments	After the subject is discharged from the unit, any changes to the antidepressant or antianxiety medication regimen are not prohibited, but investigators are encouraged to maintain such drugs at stable doses if possible. Any changes	After the subject completes the study treatment period , any changes to the antidepressant or antianxiety medication regimen are not prohibited, but investigators are encouraged to maintain such drugs at stable doses if possible. Any changes in the

		in the medication regimen must be recorded on the concomitant medication eCRF page.	medication regimen must be recorded on the concomitant medication eCRF page.
Reason	for Change: Clarifica	tion on the timing for permitted treatments	
31	5.3.2 Prohibited Treatments	The following classes of medications and treatments are prohibited during the inpatient study period.	The following classes of medications and treatments are prohibited during the study treatment period.
Reason	for Change: Clarifica	tion on the timing for prohibited treatment	s

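### In Cohort 6 the ban on starting new psychotherapy lapses at unit discharge on Day 2, 27 days before the Day 29 primary HAMD17

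*Protocol*

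**What the plan says.** Protocol 5.3.1.1 applies one rule to all cohorts. Existing psychological treatment may continue throughout the treatment period, but "initiation of a new therapy (a new treatment modality or switching a therapist) is prohibited between screening and discharge from the inpatient unit".

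The two designs leave the unit at different times. Cohorts 1-5 are discharged at +72h (Protocol 7.3.2). Cohort 6 women are "discharged from the unit in the morning of Day 2" (Protocol 7.0), take capsules at home through Day 28 and taper on Days 29-31. The primary endpoint (Protocol 9.5.8.1) is "HAMD17 total score change from baseline to 60 hours post-infusion (on Day 3) for Cohorts 1-3 and to Day 29 for Cohort 6".

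The rules on other treatments have a different end. Protocol 5.3.2 opens with "The following classes of medications and treatments are prohibited during the study treatment period". Its list includes ECT, rTMS, vagal nerve stimulation and experimental treatments of postpartum depression, but not psychotherapy. Protocol 5.3.1.3 says "After the subject completes the study treatment period, any changes to the antidepressant or antianxiety medication regimen are not prohibited".

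On recording, Protocol 5.0 and 5.3 call for psychological care to be captured from screening to the end of follow-up, and Visits 4, 6, 7 and 8 include a review of concomitant therapies. Protocol 7.8.4, however, mentions recording only the type of counseling being received at screening. In the SAP, 12.3.2 and the Appendix 3 output list cover medications and show no output for psychological treatment.

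**The concern.** A rule that ends at discharge suits a 60-hour inpatient infusion rated before discharge. It does not suit a regimen in which nearly all treatment, and the primary rating, come after discharge. A Cohort 6 woman who is not improving at Visit 4, 6 or 7 can start CBT or change therapist before the primary rating without breaching any rule. Because that is not a protocol deviation, it would not by itself remove her from the Per Protocol set (SAP 8.2 and 9.0).

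At stake is the HAMD17 arm difference that both documents call the most influential outcome for judging efficacy, read against a marker of 3-4 points. If ganaxolone works, non-improvers will more often be on placebo, and new therapy among them would tend to lift the placebo arm. If it does not work, starts should balance in expectation, but in a cohort of about 10-30 women chance imbalance could move the difference either way. With no planned table of new starts, a reader of the study report could not tell whether this had happened.

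**Working it through.** The plan states no figure for this point, so there is none to reproduce. The check is day arithmetic on the protocol's own numbering, followed by an illustration on assumed inputs.

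**1. Does the rule cover the primary rating?**

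| | Rule ends | Primary rating | Gap |
|---|---|---|---|
| Cohorts 1-5 | +72h | +60h (Day 3) | none: 72 - 60 = 12 h to spare |
| Cohort 6 | Day 2, morning | Day 29 | 29 - 2 = 27 days |

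For the IV-only cohorts I read the endpoint as +60h from the start of infusion, because the definition places it on Day 3.

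Baseline to endpoint in Cohort 6 is 29 - 1 = 28 days, so the uncovered share is 27/28 = 96%. The SAP 8.4 window for Day 29 is Study Days 26 to 32, which gives 26 - 2 = 24 to 32 - 2 = 30 days after discharge.

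**2. Which ratings fall after the rule ends?** Cohort 6 post-baseline HAMD17 ratings through Day 29 are at +6h and on Days 2, 4, 8, 11, 15, 22 and 29, eight in all. The Day 2 rating is done before discharge. Six of eight (75%) come later. This is the same fact in another form, since only Day 29 is primary.

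**3. How much time would new therapy have to act?** From Visits 4, 6 and 7 at their nominal days: 29 - 8 = 21, 29 - 15 = 14 and 29 - 22 = 7 days.

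**4. Does another rule close the gap?** No. The 5.3.2 list omits psychotherapy, and 5.0 and 5.3 require recording without restricting anything.

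**5. Illustrative size.** Every input here is assumed.

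Bias in the arm difference = (benefit of new therapy by Day 29) x (placebo start rate - ganaxolone start rate).

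- Assumed benefit 2-4 points and 10-30 percentage points more starts on placebo: 2 x 0.10 = 0.2 to 4 x 0.30 = 1.2 points toward no effect. This does not depend on the SD or cohort size.
- Assumed SD 8. At 15 per arm, SE = 8 x sqrt(2/15) = 2.92, so the bias is 0.07 to 0.41 SE. At 5 per arm, SE = 8 x sqrt(2/5) = 5.06, so it is 0.04 to 0.24 SE.
- Assumed true difference 3.5. The chance of observing at least 3 points at 15 per arm is 57% with no bias, 54% with 0.2 and 41% with 1.2. At 5 per arm it moves from 54% to about 45% at the extreme.
- Excess placebo starters needed for a full 1-point loss at 15 per arm: 15/4 = 3.75 to 15/2 = 7.5, so about 4 to 8 women.

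**6. After the fix.** If the rule ran through the Visit 8 assessments, the uncovered interval before the primary rating would be 0 days, apart from starts allowed for clinical need.

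**The case against.** **Efficacy here is hypothesis-generating.** The trial is unpowered and does not control type 1 error, and the likely bias is toward no effect, so it would not manufacture a signal. This stands and keeps the point below critical. It does not remove the point: Protocol 2.1 says the results will be used to select a dose and regimen for further development, and an understated difference can misdirect that choice.

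**A clinical-need exception lets through the starts that matter most.** Women enter with HAMD17 of at least 26 at screening and 22 on Day 0, so non-improvers are the likeliest to qualify. This largely stands. The extended rule would mainly stop elective starts, which is why the by-arm table is needed as well.

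**Open access at home fits the add-on design**, which Protocol 3.5 justifies as limiting risk. That is a fair reason for the exception, but neither document offers it as a reason for ending the rule at discharge.

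**Stronger readings that a reader might infer:**

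- *That 5.3.1.3 expressly bans antidepressant changes during treatment.* It only says changes are not prohibited afterwards, so the earlier restriction is implied. The explicit parallel is 5.3.2.
- *That the change log proves an oversight.* The Amendment 7 summary shows that those two rules previously ended with "After the subject is discharged from the unit, any changes to the antidepressant or antianxiety medication regimen are not prohibited" and "The following classes of medications and treatments are prohibited during the inpatient study period", and were moved to the treatment period. That is superseded text and only history. It does not show whether leaving 5.3.1.1 alone was deliberate.
- *That the plan contains no relevant analysis at all.* The exploratory endpoint sections (Protocol 9.5.8.3, SAP 12.5.3) show headings without content. What can be said is that the readable text and the Appendix 3 list contain nothing on psychological treatment.
- *That exclusion 16, which also ends at discharge, is a second instance.* It tests willingness at entry, and 5.3.2 with Appendix 1 separately bans grapefruit juice through treatment. A woman can satisfy both, so there is no conflict.

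**Conclusion.** The gap is real and specific to Cohort 6. The rule on new psychotherapy stops 27 days before the nominal primary rating, or 24 to 30 days across the analysis window. In the IV-only cohorts it covers the endpoint, and the explicit 5.3.2 bans last through treatment. The day counts rest only on the documents.

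The consequence is a possible blurring of the Cohort 6 arm difference, probably toward no effect. That direction assumes that ganaxolone works, that non-improvers seek new therapy more often, and that therapy helps within one to three weeks. A reader might infer that the gap could hide a true 3-4 point difference. The documents do not support that: they give no start rate, benefit or SD. On the assumed inputs the loss is 0.2-1.2 points, and a 1-point loss needs a large excess of placebo starters. The effect is probably modest. The change is worth making because it is cheap and bears on the outcome the plan weighs most.

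**What to change.** **Protocol 5.3.1.1.** Keep discharge as the end for Cohorts 1-5. For Cohort 6, prohibit a new modality or therapist switch from screening through completion of the Visit 8 (Day 29) assessments, except where the investigator judges a start clinically needed. Record such starts with date and reason, and do not withdraw the woman. Tying the rule to the visit covers a rating as late as Day 32, one day after the last taper dose on Day 31.

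**Protocol 7.8.4 and the eCRF.** Align 7.8.4 with 5.3 so that psychological treatment is recorded throughout, not only at screening. Confirm that the eCRF page captures start dates: the SAP cites a CRF dated 09Aug2018, before the 08Oct2018 protocol amendment.

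**SAP.** Tabulate by arm any new psychological treatment started before Visit 8. Optionally, rerun the Cohort 6 MMRM with HAMD17 ratings after such a start set to missing. Do not add the placebo-based imputation of SAP 12.5 to that run. Its model would carry baseline plus eight post-baseline ratings, 1 + 8 = 9 HAMD17 variables through Day 29 (12 with Days 36, 57 and 71), fitted to 15 or fewer placebo subjects with some ratings removed.

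**Cost.** Two short protocol edits, an eCRF check (a start-date field if it is missing), one table and an optional rerun, with no new visit. The real downside is asking depressed women to defer elective new psychotherapy for about four weeks. The exception softens this, and continuing therapy is untouched.

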#### 5.3.1.2 Permitted Antidepressant Treatments

The subject may continue their current SSRI, SNRI or bupropion or other serotonin or norepinephrine modulating antidepressant (e.g. vortioxetine, mirtazapine) treatment provided the regimen conforms to the standard of care and the medication was started at least 21 days before the screening visit, and there has not been a dose change within 7 days of the screening visit. The antidepressant medication must have been approved for treatment of major depressive

disorder by the United States (US) Food and Drug Administration (FDA). Monoamine Inhibitors are prohibited (including all formulations of selegiline). Tricyclic antidepressant medications will be decided on a case-by-case basis with the medical monitor.

#### 5.3.1.3 Other Permitted Treatments

The subject may continue her current non-psychiatric medications with the exception of medications that are strong inducers or inhibitors of CYP3A4 (Appendix 1).

The subject may use diphenhydramine 25 to 50 mg, trazodone 25 to 50 mg or doxepin 3 to 5 mg during the inpatient or outpatient phase for severe insomnia as needed. Only 1 dose of 1 of the medications is allowed per night. It is recommended to use the same medication each night. To minimize carryover effects there should be a minimum of 10-hour interval between administration of an allowed hypnotic and any efficacy assessment. Other hypnotics, such as zolpidem or zaleplon, are prohibited.

If the subject is treated with an atypical antipsychotic medication that was started with the purpose of augmenting the therapeutic effect of an antidepressant (i.e. the antipsychotic is not intended for treatment of psychosis or mood stabilization), she may continue this treatment throughout the study period. Examples of such treatments would be quetiapine 50 mg at bedtime and aripiprazole 15 mg daily. However, the antipsychotic medication must have been started at least 21 days before the screening, and there should not have been a dose change within 7 days of screening.

Other medications and medication combinations should be discussed with the medical monitor before enrolling the subject in the study.

After the subject completes the study treatment period, any changes to the antidepressant or antianxiety medication regimen are not prohibited, but investigators are encouraged to maintain such drugs at stable doses if possible. Any changes in the medication regimen must be recorded on the concomitant medication eCRF page.

